2.1. Primary Objective

Reduce coughing episodes in IPF patients by 25%. (An episode is defined as 5 or more coughs per hour.)

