5.1. Pre-study

Individuals with a clinical diagnosis of idiopathic pulmonary fibrosis (as defined by the WHO and the Thoracic Society) will be solicited for participation in this phase 3 trial. After signing the informed consent, participants will be randomly assigned to either the placebo or drug groups in a double-blinded randomized fashion. On pre-study day 1 (Screening Visit), and, after signing the informed consent, they will have their degree of nasal inflammation and erythema, nasal cellular morphology, SaO₂, and FEV₁, and FVC levels recorded (baseline). All subjects will have a blood sample taken, and women of child-bearing age will provide a urine sample. The subjects will fill out a quality of life questionnaire (chronic respiratory disease questionnaire (CRDQ), and they will be given a data logbook in which they will record the number of coughs they experience each day for 7 days until they return to the clinic to begin the study (baseline). Any subject who is not compliant $\geq 80\%$ will not be entered into the trial.

Blood will be analyzed for CBCs, and for standard clinical variables, including urea nitrogen, serum creatinine, total protein, serum albumin, total globulin, albumin/globulin ratio, total bilirubin, alkaline phosphatase, aspartate aminotransferase (AST or SGOT), Alanine Aminotransferase (ALT or SGPT), Lactate Dehydrogenase (LDH), Gamma-glutamyl Transferase (GGT), Serum Sodium, Potassium, Chloride Serum, Carbon Dioxide, C-reactive protein, and Total Cholesterol:HDL Ratio to determine organ health. Subjects may not enter the study until the blood and urine samples are analyzed and evaluated to confirm that subjects do not have a metabolic abnormality that would prevent entry, and that women are not pregnant.

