5.2. Study Days

Following the 7-day pre-study period, which includes time for analysis of the blood and urine, eligible IPF patients will return to the clinic and be admitted to the 21-day study. On the first day of the study, these patients will have a physical exam and their vital signs will be recorded. Then, their degree of nasal inflammation and erythema will be evaluated and recorded as before, as will their SaO2, FEV1 and FVC levels and frequency of coughing. Patients will be instructed on how to self-administer their first dose of the nasal spray drug (0.2% sodium pyruvate in 0.9% sodium chloride solution) by first forcefully expelling air from their lungs, and

then spraying 3 squirts of the drug into each nostril, and then forcefully inhaling the drug so that the drug is inhaled into the lungs. After 1 hour, the subjects will have their vital signs taken again. Efficacy and safety evaluations will occur at this 1-hour time period, too, and then again at 2 and 3 hours. The subjects will fill out the product evaluation questionnaire, be given a daily data log form and be given enough drug to last for 21 days (3 bottles), and released from the clinic.

For the next 21 days, subjects will self-administer 3 squirts per nostril of the nasal spray, as instructed, 3 times daily; upon wakening, noon/midday, and before bedtime, Additionally, they will fill out the Daily Data Log form each day to record the number of daily coughs. Patients will be contacted by phone every 2 days to review symptoms and protocol compliance.

On days 8, 14 and 22, they will return to the clinic and have their blood analyzed, vital signs taken, and their degree of nasal inflammation, erythema and cellular morphology recorded. As before, they will be tested for FEV_1 , FVC and SaO_2 levels. The number of coughs they experienced and other information will be discussed with the clinician. They will fill out the product evaluation questionnaire and the CRDQ, and they will then be released from the study on day 22. These data will then be evaluated.

6. Criteria for Patient Selection, Exclusion of Patients, and Number of Patients 6.1. Subject Selection and Number of Patients to be Studied

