The investigator is to record the use of all concomitant medications, both prescribed and over the counter (OTC) (including but not limited to natural food supplements), in the CRF. Subjects may continue to use their normal therapy as long as they list it as a current medication, and it is not prohibited by the exclusion criteria. Allowable concomitant therapy includes antiviral, antibiotic, antimicrobial, corticosteroids, antihistamines, or anti-inflammatory medications. The clinician may prescribe "rescue medication" should it be required by any of the patients. Patients may continue taking nutritional supplements as long as they do not contain pyruvate.

Subjects may not use any of the following during the trial or for 1 week before enrollment in the trial: all intranasal medications or lavages.

12. The Planned Maximum Dosage, and the Duration of Individual Patient Exposure to the Drug

This is a constant dose study. The amount of delivered sodium pyruvate was determined in prior clinical trials to be 3 sprays of 0.2% (2.2 mg/mL) sodium pyruvate in 0.9% sodium chloride solution per nostril, 3 times per day. The dose was determined by evaluating the data from both animal and human studies (cited above). Patients will forcibly expel air from their lungs and then will administer 3 sprays per nostril while inhaling strongly so that the drug is transported through the nose and into the lungs. The drug is to be administered 3 times per day (morning, mid-day, and evening). The product comes with instructions for administration (3 sprays per nostril).

13. A Description of the Observations and Measurements to be Made to Fulfill the Objectives of the Study

Observations for safety will include a pregnancy test for women of child-bearing age, blood tests for organ function, and vital signs. Adverse events will be monitored.

Observations for efficacy will include evaluation of lung function, as determined by FEV₁, FVC, nasal inflammation and erythema, and number of daily coughs.

13.1. Testing Schedule

Test	Screening	Day 1; 0,1,2,3 Hours	Day 8	Day 14	Day 22
Clinic Visit	+	+	+	+	+
Informed Consent	+				
Medical History	+				
Physical Exam/	+	+		+	+
Product Eval Q	+			+	+
CDRQ	+		+	+	+
Administer Drug		+	+	+	+
Blood Sample	+			+	+
Vital Signs	+	+	+	+	+
Pregnancy Test for Females	+				
Concurrent Medications Taken	+	+	+	+	+
SaO ₂	+	+	+	+	+
Nasal Inflammation	+	+	+	+	+
FEV ₁	+	+	+	+	+
FVC	+	+	+	+	+
Coughing Data Logbook*	+	+	+	+	+

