Adverse Events			+	+	+
Phase Product Evaluation.	+	+	+	+	+

*The coughing data logbook will be filled out by the patient every day, starting at the pre-study visit through day 14.

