In the case of a subject lost to follow-up, attempts to contact the subject must be made and documented in the subject's medical records.

Withdrawn subjects will not be replaced.

15. A Description of Clinical Procedures, Laboratory Tests, or Other Measures to be Taken to Monitor the Effects of the Drug in Human Subjects and to Minimize Risk

Tests and analyses will be conducted 3 times during the study. If any aberrant values occur, the principal investigator will determine if that patient should continue in the study or be removed. All aberrant values that occur during the study will be considered adverse events. A summary of possible risks will be provided to the patients. Previous risks of using the product are minimal, which included irritation to the nose cavity reported by 1 patient out of 1,869.

16. Safety Precautions Included in this Study

The 0.2% nasal sodium pyruvate inhalation has been administered to both healthy humans and humans with lung diseases, without the occurrence of any SAE.

- First administration of nasal spray on the premises of a hospital/clinic.
- The initial nasal spray will be administered under the supervision of medical staff.
- If a subject develops any adverse event during the follow-up period after study drug administration, the subject will be treated to a satisfactory resolution before being discharged from the clinic.
- Subjects will remain at the test site for monitoring for 30 minutes after the initial inhalation of the nasal spray.
- Follow up telephone communications, as needed.

17. Product Evaluation Questionnaire

This self-administered questionnaire measures the patients' impressions of how the drug affected their nasal cavity, their coughing, and their breathing. It is designed to evaluate changes in a subject's quality of life over time. It will be administered during all clinic visits.

18. Daily Data Logbook

Subjects will use this diary card to record the number of their coughs per day, any self-perceived adverse events, and any medication changes during the study.

19. Urinalysis

Samples will be taken and analyzed to determine if any child-bearing females are pregnant.

20. Study Management

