20.2. Data Collection, Management, and Statistical Analysis

The data management staff at the research clinic will collect and manage the data. Data will be obtained, maintained, and transmitted securely in accordance with HIPAA guidelines. Monitoring and auditing of the data will be conducted by a staff member of Cellular Sciences.

Statistical analysis will be performed on deidentified data. The basic statistical analysis will be repeated measurements of Analysis of Variance using baseline measurements as a covariant (ANCOVA). Age, sex, time since initial diagnosis with IPF, concurrent medications and smoking status are considered potential covariates. Number of coughing episodes reported for a 24-hour pre-study period, and other pre-study data information, will be compared to the data collected during the trial. The differences between baseline data and the data collected during the trial will be compared and analyzed (Within treatment). Additionally, the data of the patients on the experimental therapy will be compared to the data generated by the patients on placebo (Between treatments). P values of <0.5 will be considered significant. FEV1 and FVC will similarly be analyzed as secondary outcome measurements. Relative changes will be analyzed by JMP, Matillion, XLSTAT or R software by [name] or [name], who will be responsible for the statistical analysis.

Partial patient data will be included in the statistical analysis if patients withdraw from the study, but data from non-compliant patients will be excluded. Our previous research (REF) indicates that a sample size of 20 is sufficient to detect a statistically significant difference (p<0.05) between treatment groups. We have chosen to enroll 25 patients in each treatment group to ensure we achieve the necessary sample size, taking into account that some patients may not complete the study, and some data will be incomplete or excluded from the study.

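### The primary endpoint counts hours with five or more coughs, but the diary is described as recording only a daily total, so the endpoint cannot be derived

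*Combined protocol and SAP*

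**What the plan says.** **Endpoint.** Section 2.1 aims for a 25% reduction in coughing episodes and adds: "An episode is defined as 5 or more coughs per hour". Section 20.2 keeps the same unit for the baseline side of the comparison: "Number of coughing episodes reported for a 24-hour pre-study period".

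**Data collected.** Four sections describe the cough record, all in coughs per day:

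- Section 5.1, baseline logbook: patients "record the number of coughs they experience each day for 7 days".
- Section 5.2, on treatment: patients "fill out the Daily Data Log form each day to record the number of daily coughs".
- Section 13, efficacy observations: the list ends with "nasal inflammation and erythema, and number of daily coughs".
- Section 18, diary: "Subjects will use this diary card to record the number of their coughs per day".

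The only other cough measure is taken in clinic on day 1 (Section 5.2), where the list of assessments ends with "FVC levels and frequency of coughing". No unit or method is given.

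**Duration.** The footnote to the schedule in Section 13.1 has the logbook completed daily "starting at the pre-study visit through day 14", whereas Section 5.2 describes a daily log over 21 days.

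**The concern.** An endpoint with an hourly threshold needs hourly counts. The text describes no hourly field, time stamp or cough monitor, and no conversion rule. Hourly timing that is not written down on the day cannot be recovered later.

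If the trial runs as described, the analysts will have to replace episodes with something else, most likely the daily count, once the data are in. The 25% target would then mean something different, and the primary analysis of a trial described as phase 3 would no longer be prespecified.

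A floor effect is also possible. Eligibility requires a condition-related cough but sets no minimum count, so some patients may have no episode at baseline and no room to improve on this endpoint.

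**Working it through.** **1. The stated sample size.** Section 20.2 says 20 patients suffice and 25 per group will be enrolled. This cannot be reproduced, because no SD, effect, power or dropout rate is given. Reading 20 as per arm, 80% power at two-sided 0.05 needs a standardised difference of (1.960 + 0.842) × √(2/20) = 0.886. The 25 equals 20/(1 − 0.20), but no 20% loss is stated.

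**2. Bounds on episodes for a daily total T (no model needed).** The maximum is the smaller of 24 and floor(T/5). The minimum is 0 whenever T ≤ 24 × 4 = 96, since four coughs in every hour never reach the threshold.

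| Coughs per day | Mean per hour (T/24) | Possible episodes |
|---|---|---|
| 4 | 0.17 | 0 |
| 15 | 0.63 | 0 to 3 |
| 30 | 1.25 | 0 to 6 |
| 57 | 2.38 | 0 to 11 |

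The rows for 4 and 57 are the ends of the range in Section 1.1.6. Only totals below 5 fix the answer, at zero. Reading the definition as a 24-hour average does not help: it needs 5 × 24 = 120 coughs per day, more than twice the top of that range.

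**3. Percentage changes do not convert.**

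- Six hours of 5 coughs (30), each losing one, become six hours of 4 (24). Coughs fall by 6/30 = 20%; episodes fall from 6 to 0, which is 100%.
- Three hours of 10 coughs (30), halved, become three hours of 5 (15). Coughs fall by 50%; episodes stay at 3, a 0% fall.

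**4. Floor effect (illustrative; depends on assumptions).** I assume a 16-hour day and the 14.6 : 1.9 day-to-night rate ratio from Section 1.1.6. Only the ratio is borrowed, because those rates imply 14.6 × 16 + 1.9 × 8 ≈ 249 coughs per 24 hours, a heavier-coughing group. If p(d) and p(n) are the chances of at most 4 coughs in a day hour and a night hour, the chance of no episode in 7 baseline days is [p(d)^16 × p(n)^8]^7. At 15 coughs per day the hourly means are 0.88 and 0.11.

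| Timing of coughs | Chance of no episode in 7 days, 15/day |
|---|---|
| Random (Poisson) | 79% |
| Negative binomial, shape 2 | 26% |
| Shape 1 | 8% |
| Shape 0.5 (strongly clustered) | 1% |

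At 30 per day the chance is about 2% with random timing and near 0% with clustering. At 57 per day it is near 0% throughout. Under the same assumptions, 25% fewer coughs means from 25% fewer episodes (57/day, shape 0.5) to 72% fewer (15/day, random), so no single conversion factor exists.

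**5. Power if the daily count becomes the endpoint.** Two-sample t-test, two-sided 0.05, effect |ln 0.75| = 0.288 on the log scale. The SD is that of the baseline-adjusted log mean count. The documents give none, so these values are assumptions.

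| SD | 20 per arm | 25 per arm |
|---|---|---|
| 0.3 | 84% | 91% |
| 0.4 | 60% | 70% |
| 0.5 | 43% | 51% |
| 0.6 | 32% | 38% |

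The largest SD that gives 80% power is about 0.32 with 20 per arm and 0.36 with 25. I used 0.05 because the sample-size sentence does; the significance rule in the same section is printed as 0.5, which is a separate point.

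**The case against.** The strongest reply is that the diary form and case report forms are not in the text, and some pages just before Section 5.1 were also unavailable. Section 20.2 speaks of episodes being reported, which would fit a form that asks for them directly. This limits the finding to the collection as described. It does not remove it: four sections say coughs per day, and if an hourly form exists the protocol has to say so.

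The floor effect is also a fair target. It is pronounced only near the bottom of the cited range, fades by 30 coughs per day, and depends on assumed clustering. It should be read as a possibility of unknown size. The bounds in step 2 do not depend on it.

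Finally, the mismatch could be cured from either side. Moving to the daily count gives up the sponsor's own endpoint. A between-arm target also settles something the plan leaves open: Section 2.1 gives no reference for the 25%, and Section 20.2 lists both within-arm and between-arm comparisons. Both are choices and should be acknowledged as such. I prefer them because the daily data are already planned and the trial is randomised against placebo.

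**Conclusion.** The concern holds. On the protocol's own description, the primary endpoint cannot be computed from the data collected. For any patient with 5 to 57 coughs per day, the diary total is compatible with anything from no episodes to floor(T/5), which is 11 at the top of the range. No percentage change in coughs determines the percentage change in episodes.

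This conclusion needs no distributional assumption. It rests on the diary matching its description in Sections 5.1, 5.2, 13 and 18. The clustering and power figures do rest on assumptions and are secondary. The point must be fixed before enrolment, because the missing timing cannot be reconstructed.

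**What to change.** **Preferred change.** Restate Sections 2.1 and 20.2 so that the primary endpoint is the mean daily diary cough count over a prespecified on-treatment window. Compare arms with the 7-day baseline mean as covariate, on the log scale or with a negative binomial model. State the 25% target as a between-arm ratio of 0.75, and say explicitly that this is the chosen reference.

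**Reconcile first.**

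- Logbook duration: the Section 13.1 footnote (to day 14) against Section 5.2 (21 days). If the log runs 21 days, the window can be days 15 to 21; if it stops at day 14, days 8 to 14.
- Baseline: 24 hours in Section 20.2 against 7 days in Section 5.1.

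**Sample size.** Section 20.2 must say that its figure of 20 refers to the daily count, whether it is per arm, and what SD, power and dropout it assumes.

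**Cost.** Text edits to Sections 2.1 and 20.2 and the Section 13.1 footnote. If the logbook really stops at day 14, a days 15 to 21 window adds 7 diary days per patient; a days 8 to 14 window adds none. The episode concept is lost, and 25 per arm may prove too few if the SD exceeds about 0.36.

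**Alternative.** Keep episodes and have the diary record coughs by hour, at baseline and on treatment, with the sample size justified for that endpoint. This preserves the stated objective at the price of a heavier burden on patients.

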1.1.6. Prior Sodium Pyruvate Treatment in Pulmonary Fibrosis and IPF Studies

A phase 2 study was designed to demonstrate safety, efficacy, and determine which medical endpoints produced clinically and statistically significant results. Inflammatory pathways are upregulated in the nasal epithelium in 80% of patients with IPF, which is part of the etiology of

the disease that effects all lung functions (28). Inflammation induced oxidative stress decreases lung functions including FEV_1 and FVC values and increases mucus and coughing. Nasal steroids and OTC products have been ineffective in treating these conditions in IPF patients, especially when these patients experience exacerbation do to stress or allergies.

Coughing frequency is high in patients with advanced IPF, with median (range) 24-h cough counts varying from 226 (36–946) to 520 (117–1493) depending on the population studied (34-41). In mild to moderate cases in IPF patients, cough counts vary from 4-57 per 24-h. Strikingly, IPF patients experience more cough symptoms during the daytime (median hourly cough rate 14.6 during the day versus 1.9 during the night) (34-41). Chronic cough in IPF is not related to age or gender and is more common in advanced disease and in "never-smokers" (34-41). There is no clear explanation why IPF patients without a history of smoking cough more.

An initial 21-day sub-chronic clinical trial was conducted that included 15 patients with pulmonary fibrosis (9 with pulmonary fibrosis and chronic obstructive pulmonary disease (COPD) and 6 with idiopathic pulmonary fibrosis without COPD) that remained on their normal medications, but were also administered the 20 mM (2.2 mg/mL) sodium pyruvate nasal spray. If the patients were using other nasal sprays as part of their normal therapy, the other nasal spray was eliminated. In all 15 patients, the test results were compared to their previous 3-week screening and baseline data (their current therapies) as the positive control for each variable including all their lung functions, FEV₁, FVC, PEF, FEV₁/FVC ratios, SaO₂, nitric oxide, coughing rates and nasal inflammation (23).

Results

Coughing

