The patient population is adult patients \geq 40 years old with mild to moderate IPF with FVC and FEV1 values \geq 50% of predicted values. IPF is defined in accordance with the most recent collaborative guidelines from the American Thoracic Society, the European Respiratory Society, the Japanese Respiratory Society, and the Latin American Thoracic Association (56) including HRCT scan and/or lung biopsy consistent with unusual interstitial pneumonia (UIP), especially honeycombing, without identifiable cause related to other ILD such as drug toxicity, occupational or environmental exposure or connective tissue disease.

The study goal will be to enroll 25 patients with confirmed IPF into the trial in the sodium pyruvate (N115) treatment group and 25 with confirmed IPF to be enrolled in the trial in the placebo group. Efforts will be made to include women and minorities. The study will be a randomized, double-blinded placebo-controlled trial to subjects and study investigators.

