6.2. Inclusion Criteria

- Individuals with a clinical diagnosis of idiopathic pulmonary fibrosis as determined by clinical evaluation and lung function tests (56), with a condition-related cough.
- Mild to moderate FEV₁ and FVC at 50% or greater of standard
- Individuals who agree to abstain from sexual intercourse, or agree to use condoms or vaginal diaphragms or other devices designed to prevent contraception, during the entire course of the study.

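### The primary measure counts only hours with 5 or more coughs, which suits the enrolled mild-to-moderate patients poorly: many may have no baseline episode, and 25% fewer episodes is not 25% less cough

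*Combined protocol and SAP*

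**What the plan says.** **Measure.** The primary objective (Section 2.1) is to "Reduce coughing episodes in IPF patients by 25" per cent, and "An episode is defined as 5 or more coughs per hour". The section does not say whether the reduction is against baseline or against placebo, or per patient or per group.

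**Population.** Section 6.1 enrols patients "with mild to moderate IPF with FVC and FEV1 values" at or above half of predicted. Section 1.1.6 describes that group: "In mild to moderate cases in IPF patients, cough counts vary from 4-57 per 24-h". For advanced disease the same section gives medians of 226 to 520 per 24 hours.

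**Entry.** The only cough criterion in Section 6.2 is a diagnosis "with a condition-related cough". Section 6.3 sets no minimum either. The 80% rule in Section 5.1 concerns compliance.

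**Data and analysis.** The diary (Sections 5.1, 5.2 and 18) records coughs per day, and Section 13 names the daily number of coughs as the efficacy observation. Section 20.2 plans a repeated-measures ANCOVA with baseline as covariate, and compares trial data with episodes from one 24-hour pre-study period.

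**The concern.** The threshold is 5 in one hour. The enrolled group averages at most about half of that. Nothing at entry ensures that a patient has any episode to lose, and an episode baseline of zero can only stay level or rise. With 25 patients per arm, a sizeable zero group would cost precision on the sole primary endpoint.

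The threshold also changes the meaning of the target. Episodes are a non-linear function of cough rate, so a given percentage fall in episodes corresponds to a different percentage fall in cough, and the relation varies with how much a patient coughs. A result of 25% fewer episodes could not be read as 25% less cough.

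Recording coughs by the hour would make episodes measurable, which a daily count does not, but it would not remove either problem.

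**Working it through.** **Steps that need few or no assumptions**

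- Mean hourly rate: 4/24 = 0.17 to 57/24 = 2.4. If every cough fell in an assumed 16 waking hours: 4/16 = 0.25 to 57/16 = 3.6. Both ranges are below 5.
- Most episodes possible in a day (coughs divided by 5, rounded down): 0 at 4 coughs, 2 at 10, 4 at 20, 11 at 57.

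**Model for the share with no episode**

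From the documents: the 4-57 range, the threshold of 5, and the day/night contrast ("median hourly cough rate 14.6 during the day versus 1.9 during the night"), used only as a ratio. Assumed: 16 waking hours; hourly counts either Poisson or, to allow for clustering, negative binomial with k = 1 or 0.5; patients spread over 4-57 either uniformly or log-uniformly.

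For a patient with c coughs per day, the waking rate is d = c / (16 + 8 × 1.9/14.6) = c / 17.04 and the night rate is n = d × 1.9/14.6. Then:

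- expected episodes per day = 16·P(X_d ≥ 5) + 8·P(X_n ≥ 5)
- chance of no episode in 24 hours = [1 − P(X_d ≥ 5)]^16 × [1 − P(X_n ≥ 5)]^8, raised to the power 7 for the full diary week.

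| Coughs/day | d per hour | Episodes/day (Poisson; k=1; k=0.5) | Chance of none in 24 h (same order) |
|---|---|---|---|
| 10 | 0.59 | 0.006; 0.11; 0.25 | 99%; 90%; 78% |
| 20 | 1.17 | 0.11; 0.73; 1.06 | 89%; 47%; 34% |
| 40 | 2.35 | 1.4; 2.7; 2.8 | 22%; 5%; 5% |
| 57 | 3.34 | 3.9; 4.4; 4.1 | 1%; 1%; 1% |

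Averaged over the range:

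| Spread | None in 24 h (Poisson; k=1; k=0.5) | None in 7 days (same order) |
|---|---|---|
| Uniform | 54%; 32%; 27% | 29%; 11%; 7% |
| Log-uniform | 77%; 58%; 51% | 58%; 32%; 21% |

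Of 25 patients per arm, 27% is about 7 and 77% is about 19.

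**What a true 25% fall in cough looks like**

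Multiply every rate by 0.75 and recompute. The fall in total group episodes is 60-61% (Poisson), 38-40% (k=1) and 31-34% (k=0.5). For single patients it is 35-66% at 30 coughs per day and 25-55% at 57.

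Replacing 16 waking hours by 14 or 18 in the same formulas moves the three ranges only to 26-79% (none in 24 hours), 6-60% (none in 7 days) and 30-62% (group fall).

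**Precision, as illustration only**

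Section 20.2 says that 20 patients suffice but gives no effect size, SD or power, so that figure cannot be reproduced. Suppose 20 per arm gave 80% power at two-sided 0.05, which needs a standardized difference of √(2/20) × (1.96 + 0.84) = 0.89. If 25% of patients carry no information, 15 per arm remain and power is 68%. If they stay in and dilute the mean difference to 0.75 × 0.89 with the same SD, power is 56%.

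**The case against.** Several points against a stronger reading stand.

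- **A reader might infer that enrolled patients cannot have episodes.** The range is per day and the threshold per hour, so it lies below the threshold only on average. Coughs cluster, and a patient near 57 per day would be expected to have about 4 episodes a day.
- **A reader might infer that the analysis breaks down at a zero baseline.** It does not. A per-patient percentage would be undefined, but Section 2.1 states one target for the patients as a group, and an ANCOVA with baseline as covariate can be computed with zeros.
- **A reader might infer that an effective drug would miss the target.** The model points the other way for the group percentage: every scenario exceeds 25%. The harm is lost precision and a misleading scale, not a target out of reach.
- **A reader might add that heavy coughers saturate the measure.** The hourly medians of 14.6 and 1.9 imply 16 × 14.6 + 8 × 1.9 = about 249 coughs a day, more than four times the upper end for the enrolled group. That argument does not concern this population.

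The size is also uncertain. The documents give a range and no distribution, and the coughing results of the earlier study in Section 1.1.6 are missing from the copy reviewed. A zero on one day is also not a patient who never has episodes, as the gap between the 24-hour and 7-day shares shows.

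None of this removes the mismatch. Even the most favourable scenario leaves about a quarter of patients at zero on the baseline that Section 20.2 specifies.

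**Conclusion.** The concern holds as a mismatch between the primary measure and the enrolled population. The averages of 0.2-2.4 coughs per hour and the absence of a cough minimum come straight from the documents. The shares with no baseline episode (27-77% on 24 hours, 7-58% on 7 days) and the 31-61% fall in group episodes for a true 25% fall in cough rest on the assumed waking hours, clustering and spread. They should be read as ranges, not estimates.

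The consequences are reduced precision and a 25% target that does not mean 25% less cough. The documents do not support the claims that episodes are impossible, that the ANCOVA is undefined or that the trial must fail. The point should be settled before enrolment because it concerns the only primary endpoint.

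**What to change.** - **Section 2.1:** attach the 25% target to the mean daily cough count, and say whether it is measured against baseline or against placebo.
- **Section 20.2:** analyse that count by the planned repeated-measures ANCOVA, with the mean of the 7-day pre-study diary as baseline in place of one 24-hour period.
- **Episodes:** report any 5-per-hour measure as supportive only. It would need hourly recording.

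No new procedure is needed for the main change, because the diary already collects daily counts. Section 5.2 has the diary filled in over the 21 days, while the footnote to the Section 13.1 schedule ends it at day 14. Those two must be reconciled so that the count covers the intended period. The real cost is that the primary measure changes from episodes to counts and is no longer comparable with any earlier episode data.

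A minimum baseline cough is an optional design choice and not part of this fix. With a minimum of 15-20 coughs per day, for example, the share excluded would be (15 − 4)/53 to (20 − 4)/53 = 21-30% under a uniform spread. Under a log-uniform spread it would be ln(15/4)/ln(57/4) to ln(20/4)/ln(57/4) = 50-61%. The documents give no source for such a cut-off. It would also require randomisation to follow the diary week, whereas Section 5.1 places assignment directly after consent.
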